The robustness of the results of the primary analysis for the effect of the missing mechanism will be checked using a placebo multiple imputation method and a pattern mixing model (including a shift parameter analysis)³⁶⁾ that assumes a missing not at random missing mechanism. A more detailed description of the analysis method will be presented in the SAP.

• Supplementary analysis with respect to the data pooling on 1 mg q4w and placebo

The data on 1 mg q4w and placebo obtained before and after the protocol amendment (Ver. 04.00.00000) will be analyzed using the same method as for the primary analysis to confirm the data homogeneity and the robustness of the results of the primary analysis. Also, homogeneity in demographic and other baseline characteristics [Section 13.3.1] between data obtained before and after the protocol amendment will be confirmed.

(2) Analysis of the key secondary efficacy endpoint

Analyses similar to those described in primary analysis (a) will be performed for the change in the WOMAC physical function score and the change in the PGA from baseline to Week 16, the key secondary efficacy endpoint.

Because this study is a confirmatory study, in order to keep the family wise type 1 error rate to a significance level of 5% (alpha), two-sided, in the tests of the following hypotheses regarding the primary endpoint and the key secondary efficacy endpoint, a gatekeeping method³⁷⁾ based on a graphical approach will be used to perform multiplicity adjustment, as shown in Figure 13.3.2.1 to verify the hypotheses.

This multiplicity adjustment will only be performed for the statistical analyses of data from the double-blind period from screening to Week 16 after treatment initiation.

- Null hypothesis H01: The change from baseline in the WOMAC pain subscale at Week 16 in the 1 mg SC q4w group is the same as that in the placebo group
- Null hypothesis H02: The change from baseline in the WOMAC pain subscale at Week 16 in the 1 mg SC q8w group is the same as that in the placebo group
- Null hypothesis H03: The change from baseline in the WOMAC physical subscale at Week 16 in the 1 mg SC q4w group is the same as that in the placebo group
- Null hypothesis H04: The change from baseline in the WOMAC physical subscale at Week 16 in the 1 mg SC q8w group is the same as that in the placebo group

[figure not shown]

Figure 13.3.2-1: MT-5547 Multiple Test Procedure

(3) Analysis of Secondary Endpoints

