Because this study is being conducted as a placebo-controlled study, in order to detect a statistical difference between the MT-5547 groups and the placebo group, the mean intergroup difference relative to placebo in both the change from baseline in the WOMAC pain subscale score and the change from baseline in the physical function subscale score at Week 16 for the MT-5547 3 mg SC q4w, 6 mg SC q8w, and 1 mg SC q4w groups was set at 1.1, and the standard deviation 2.5, on the basis of the results obtained in the overseas P2a study (R475-PN-0901) and the overseas P2b study (R475-PN-1227) (Table 3.3-1). The effect relative to placebo in the P3 study of 5 mg and 10 mg of tanezumab, another NGF inhibitor, was 0.81 to 1.21 in the WOMAC pain subscale score and 0.98 to 1.25^{24), 25)} in the WOMAC physical function subscale score, and it therefore appears that a mean difference between the MT-5547 groups and placebo of 1.1 is a realistic assumption. It also appears that the minimum clinically significant difference in each WOMAC score will be around 0.67 to 0.75^{26), 27)}. The aforementioned intergroup difference of 1.1 exceeds the minimum clinically significant difference, and therefore seems to be an appropriate value to use for the intergroup difference. Based on a one-sided significance level of 2.5% and multiplicity adjustment based on a gate keeping method using a graphical approach, the power for MT-5547 3 mg SC q4w, 6 mg SC q8w, and 1 mg SC q4w will be 90%, 88%, and 88%, respectively, for the primary endpoint, and 82%, 79%, and 79%, respectively, for the key secondary endpoint. A 2-sample t-test will be used for the tests in each step. Based on this assumption, the number of subjects who will complete 16 weeks of treatment in each group will be 120.

Furthermore, because the proportion of missing data for the primary endpoint and the key secondary endpoint at Week 16 is around 15% according to Table 3.3-1, it is being assumed that the proportion of missing data at Week 16 will be 15%, and the number of patients per

group is therefore being set at 142.

The rationale after the changes in treatment groups

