Assuming the absolute treatment difference of 1.1 between the MT-5547 1 mg SC q8w groups and placebo in both the change from baseline in the WOMAC pain subscale score and the change from baseline in the physical function subscale score at Week 16 with an associated standard deviation of 2.5 based on the original rationale at the initiation of the study, the number of patients per group after the protocol amendment (Ver. 04.00.00000) is planned to 142 subjects per group. The structure of statistical hypotheses have been changed due to the removal of 3 mg q4w / 6 mg q8w groups and the addition of 1 mg q8w. It is noted that approximately 40 subjects per group were randomized to 1 mg q4w / placebo groups before the amendment. For evaluation on 1 mg q4w, since subjects are randomized to 1 mg q4w / placebo at the same time with the same ratio of 1:1 regardless of pre- or post-amendment, analyses will be performed with pooled comparable data including pre- and post-amendment data on 1 mg q4w / placebo (1 mg q4w group: 182 subjects; placebo group: 182 subjects). For evaluation on 1 mg q8w, analyses will be performed with only the post-amendment data (1 mg q4w group: 142 subjects; 1 mg q8w group: 142 subjects; placebo group: 142 subjects). For four null hypotheses, based on multiplicity adjustment based on a gate keeping method using a graphical approach (Figure 8.2.1-1), the power for MT-5547 1 mg SC q4w and 1 mg SC q8w will be 97% and 92% for the primary endpoint, 94% and 87% for the key secondary endpoint, respectively.

Table 3.3-1 Change From Baseline at Week 16 in the WOMAC Pain and Physical Function Subscale Scores

	REGN Study R475-PN-1227					REGN Study R475-PN-0901			
	Placebo (N=83)	MT-5547 1 mg (N=85)	MT-5547 3 mg (N=84)	MT-5547 6mg (N=85)	MT-5547 9 mg (N=84)	Placebo (N=55)	MT-5547 0.03 mg/kg (N=53)	MT-5547 0.1 mg/kg (N=53)	MT-5547 0.3 mg/kg (N=54)
Change from baseline in WOMAC pain subscale score									
Baseline	6.43	6.33	6.35	6.10	6.53	5.9	5.7	6.1	6.4
n ¹⁾	71	75	78	77	79	44	47	44	41
Mean ¹⁾ (SD) ¹⁾	-2.43 (2.38)	-3.49 (2.06)	-3.39 (2.44)	-3.07 (2.34)	-3.81 (2.49)	-2.4 (2.18)	-2.7 (1.89)	-3.4 (2.53)	-3.2 (2.24)
LSM ²⁾	-2.25	-3.35	-3.33	-3.03	-3.65	-	-	-	-
Diff. vs. Pbo ³⁾	-	-1.10	-1.08	-0.78	-1.40	-	-0.6	-1.1	-0.8

P value	-	0.0025	0.0029	0.0304	0.0001	-	0.1486	0.0090	0.0488
Change from baseline in WOMAC physical function subscale score									
Baseline	6.15	6.11	6.09	5.94	6.20	5.9	5.9	6.2	6.2
n ¹⁾	70	75	78	76	80	44	47	44	41

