6.2. Statistical Tests

Unless otherwise specified, all formal statistical tests of treatment effects will be done at two-sided significance level of 0.05. Point estimates will be accompanied with two-sided 95% CIs where applicable.

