8.2.1. Primary Efficacy Endpoint

The change in the WOMAC pain subscale score from baseline to Week 16 will be summarized and plotted by treatment group.

Primary analysis method

The primary analysis will be tested using the estimator of mixed effect model for repeated measurement (MMRM) approach. The model will include the treatment group, measurement time point, treatment group and measurement time point interaction, stratification factor K-L grade (2-3 or 4), and stratification factor evaluated joint (knee or hip) as factors, and the baseline and baseline and measurement time point interaction as covariates. The within-subject correlation structure will be unstructured, and the denominator degrees of freedom for the test statistics of estimated parameters will be approximated using the Kenward-Roger method. In case the model will not converge with the unstructured covariance structure, Heterogeneous Autoregressive (1) (ARH[1]), Heterogeneous Compound Symmetry (CSH), Autoregressive (1) (AR[1]) or Compound Symmetry(CS) covariance structure will be used instead in this order.

- Evaluation on 1 mg q4w group

[figure not shown]
With pooling the data on 1 mg q4w and placebo obtained before and after the protocol amendment (Ver. 04.00.00000), the least square mean, standard error, P value, and 95% confidence interval of the difference between each of the MT-5547 1 mg q4w and the placebo group in the change in the WOMAC pain subscale score from baseline to Week 16 will be calculated using the MMRM approach.

- Evaluation on 1 mg q8w group

Using only the data obtained after the protocol amendment (Ver. 04.00.00000), the least square mean, standard error, P value, and 95% confidence interval of the difference between each of the MT-5547 1 mg q4w, MT-5547 1 mg q8w and the placebo groups in the change in the WOMAC pain subscale score from baseline to Week 16 will be calculated using the MMRM approach.

MMRM that assumes that the missing mechanism is missing at random (MAR) is an analysis method in which missing values are not replaced. This model will be used to estimate the treatment effect in the mFAS when subjects continue receiving treatment through Week 16.

The SAS code planned for the analysis is outlined below.

Sensitivity analyses

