Each subgroup will be analyzed separately for the primary endpoint using MMRM model similar to the primary model.

Change from baseline to week 16 for the subgroup of index joint (hip or knee) and K-L score category(2-3 or 4) will be summarized by visit. Change from baseline to week 16 for the other subgroup will be summarized at week 16. In addition, forest plot depicting the treatment effect, p-values for interaction terms between the treatment group and each subgroup and 95% CI for each subgroup will be displayed.

Supplemental analysis

The PPS will be analyzed using the same method as for the primary analysis to confirm the robustness of the results of the primary analysis for the effects of the analysis set.

Supplementary analysis with respect to the data pooling on 1 mg q4w and placebo

The data on 1 mg q4w and placebo obtained before and after the protocol amendment (Ver. 04.00.00000) will be analyzed using the same method as for the primary analysis to confirm the data homogeneity and the robustness of the results of the primary analysis. Also, homogeneity in demographic and other baseline characteristics [Section 8.1.3] between data obtained before and after the protocol amendment will be confirmed.

Supplementary analysis with respect to response the site differences

Absolute values and changes from baseline will be summarized at week 16 by treatment group and site.

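### The pooled 1 mg q4w model omits amendment stage, and the planned pooling check neither compares the stages directly nor has the data to confirm that they agree

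*SAP*

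**What the plan says.** The trial began with four arms: 1 mg q4w, 3 mg q4w, 6 mg q8w and placebo (Protocol section 1, Plans for this study). Version 04 dropped the two higher-dose arms, added 1 mg q8w and randomised 1:1:1. About 40 subjects per arm were randomised to 1 mg q4w and placebo before the amendment, and 142 per arm are planned after it (SAP 3.3).

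For 1 mg q4w the primary MMRM is run "With pooling the data on 1 mg q4w and placebo obtained before and after the protocol" amendment. Pooling is justified "since subjects are randomized to 1 mg q4w / placebo at the same time with the same ratio of 1:1" on both sides of it. The listed terms are treatment, visit, treatment-by-visit, K-L grade, evaluated joint, baseline and baseline-by-visit (SAP 8.2.1; Protocol 13.3.2). Stage is not among them.

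The item that Protocol 13.3.2 lists as "Supplementary analysis with respect to the data pooling on 1 mg q4w and placebo" says that these data "will be analyzed using the same method as for the primary analysis to confirm the data homogeneity and the robustness of the results". Baseline characteristics are also to be compared across the amendment, and SAP 8.1.3 provides those tables. SAP 8.2.2 repeats the check for physical function. Neither document gives a stage-by-treatment contrast, an interval for it or a criterion. SAP 8.2.1 does plan interaction p-values for nine subgroup factors, but stage is not one of them.

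**The concern.** Allocation took place within two stages that had different arm sets. Three of four arms were active before the amendment and two of three after it, which could shift expectation and placebo response, although the documents give no data on this. The usual practice is to model the groups within which allocation was made.

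The check matters more. The plan does not say that the two stages are fitted separately, but a joint fit would only repeat the primary analysis, so separate fits are the natural reading. Two estimates side by side do not compare the stages. The smaller stage will often miss significance when the true effects are identical, and similar estimates could be reported as confirmed homogeneity when the data could not exclude a complete loss of effect in one stage. What is at stake is a statement in the study report about the pooling behind H01 and H03.

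The split is also loosely defined. SAP 8.2.1 speaks of data obtained before and after the amendment, whereas SAP 3.3 counts subjects randomised before and after it. A subject randomised before could have a Week 16 score obtained after.

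**Working it through.** **Inputs.** The difference of 1.1 comes from SAP 3.3: "Assuming the absolute treatment difference of 1.1 between the MT-5547 1 mg SC q8w groups and placebo" for the new arm, and the same 1.1 for 1 mg q4w in the original rationale there. The SD of 2.5 is also from 3.3: "with an associated standard deviation of 2.5 based on the original rationale at the initiation of the study". Missing data at Week 16 are 15% (3.3). The level is two-sided 5%: "all formal statistical tests of treatment effects will be done at two-sided significance level of 0.05" (6.2). The plan's power basis is completers: "A 2-sample t-test will be used for the tests in each step". Evaluable subjects per arm are 0.85 × 40 = 34, 0.85 × 142 ≈ 121 and 0.85 × 182 ≈ 155.

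**The plan's own figures.** Power = Φ(1.1/SE − 1.96), with SE = 2.5 × √(2/n).
- Pooled q4w, n = 155: SE 0.284, power 97.2% (stated 97%).
- q8w, n = 121: SE 0.321, power 92.8% (stated 92%).

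These ignore the multiplicity graph, whose figure is not shown. A simulated equal-split graph with an assumed pain-function correlation of 0.5 gives 96.2% and 92.1%. The inputs therefore reproduce the plan.

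**Cost of omitting stage.** With p = 40/182 = 0.220, p(1 − p) = 0.171. A between-stage shift of d points adds 0.171 × d² to a variance of 6.25.
- d = 0.5: 0.043/6.293 = 0.7% of residual variance; q4w power 97.1%.
- d = 1: 0.171/6.421 = 2.7%; q4w power 96.9%.

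The shifts are assumptions, since the documents give none.

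**Separate fits.** Before the amendment, SE = 2.5 × √(2/34) = 0.606 and power is Φ(1.815 − 1.96) = 44%. After it, power is 93%. If the true effect is 1.1 in both stages, the chance of significance after but not before is 0.928 × 0.558 = 52%.

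**Direct contrast.** SE = 2.5 × √(2/34 + 2/121) = 0.686. The 95% half-width is 1.96 × 0.686 = 1.35. Power for a stage difference of 1.1 is Φ(1.1/0.686 − 1.96) = 36%, and for 0.55 it is 13%. The difference detectable with 80% power is 2.80 × 0.686 = 1.92.

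**Sensitivity of the contrast.** The pre-amendment count is approximate. SAP 3.3 reports 57 in each dropped arm, yet its total of 563 is 506 + 57, while 57 in each would give 620. Taking 57 or 28.5 per arm as outer values:

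| Evaluable per arm, before / after | SD | SE | Half-width | Power for 1.1 vs 0 |
|---|---|---|---|---|
| 34 / 121 | 2.5 | 0.69 | 1.35 | 36% |
| 40 / 142 (no loss) | 2.5 | 0.63 | 1.24 | 41% |
| 48.5 / 121 (57 less 15%) | 2.5 | 0.60 | 1.18 | 45% |
| 24.2 / 121 (28.5 less 15%) | 2.5 | 0.79 | 1.54 | 29% |
| 34 / 121 | 2.22 | 0.61 | 1.19 | 44% |

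The last row pools the placebo and 1 mg SDs in SAP Table 3.3-1: √((2.38² + 2.06²)/2) ≈ 2.2. In every row the half-width exceeds 1.1.

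**The case against.** The best defence is that nothing confirmatory depends on this. Pooling is pre-specified, the check is labelled supplementary, and no rule abandons pooling if the stages look different. That stands, and it limits the harm to how the result is reported.

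The separate fits are also not the only safeguard. Baseline characteristics are tabulated by stage, and the q8w evaluation in SAP 8.2.1 reports 1 mg q4w against placebo on post-amendment data alone, with about 93% unadjusted power. This stands too. However, baseline tables say nothing about the treatment effect, and a post-amendment estimate is not a comparison of stages. A reader could subtract the two stage estimates and combine their standard errors, so the information would exist. What is missing is the line that reports it.

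A reader might infer three stronger things that the documents do not support:
- That omitting stage biases the q4w comparison or inflates its type I error. The 1:1 ratio in both stages rules out confounding by stage.
- That 44% is the power to detect heterogeneity. It is the power of the pre-amendment treatment test. The relevant figure is 36%, and the proposed contrast cannot establish homogeneity either.
- That stage is certainly absent from the analysis. The SAS code and the randomisation section are not visible, so only the written model can be judged.

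**Conclusion.** The point holds as an inexpensive improvement to the model and to the wording of the check. The primary test of 1 mg q4w remains valid, with power of about 97% with or without a stage term. The pooling check lacks a direct comparison of the treatment effect between stages, and it promises a confirmation that about 40 subjects per arm before the amendment cannot supply. An observed stage difference of exactly zero would still carry an interval of about −1.35 to +1.35 points, which includes a full 1.1-point loss of effect in one stage.

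This rests on the planning SD, 15% missing data and the approximate count of 40. The half-width is about 1.2 if the SD is near 2.2, and runs from 1.18 to 1.54 over the pre-amendment counts considered. The MMRM uses partial data and adjusts for baseline, so actual precision may be somewhat better than these completer figures.

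**What to change.** 1. Define stage as randomised before or after Version 04, and add stage and stage-by-visit to the pooled q4w MMRM for pain and physical function.
2. As the homogeneity assessment, fit the same model with treatment-by-stage and treatment-by-stage-by-visit added, and report the Week 16 stage-by-treatment contrast with its 95% CI. Keep the stage-specific estimates and the baseline tables as descriptive.
3. In SAP 8.2.1 and Protocol 13.3.2, replace *confirm* by *describe*.

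The cost is a few model terms and giving up the claim of confirmed homogeneity. Timing matters: the Week 16 analysis follows the Week 24 lock (Week 16 SAP 4.2), and the Week 68 SAP (4.1) describes an analysis of the Week 24 database as already done. If lock has passed, leave the pre-specified primary model as it is. Report items 1 and 2 as additional analyses under Protocol 13.4, with the reason stated and the results kept distinct from the planned ones.

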8.2.2. Key Secondary Efficacy Endpoints

The change in the WOMAC physical function subscale score from baseline to Week 16 will be analyzed on the mFAS and PPS population as the key secondary endpoint using the same primary analysis method (MMRM) and same subgroup analysis and supplementary analysis with respect the data pooling on 1mg q4w and placebo will be performed. Multiplicity adjustment described in Section 8.2.1.

8.2.3. Other Efficacy Endpoints

WOMAC pain subscale score, WOMAC physical function subscale score, WOMAC stiffness subscale score, WOMAC total score , WOMAC individual score and PGA

For the changes from baseline at each visit in the WOMAC pain subscale score, the WOMAC physical function subscale score, the WOMAC stiffness subscale score, the WOMAC total score, WOMAC individual score and PGA, the same primary analysis method (MMRM) described in Section 8.2.1 will be analyzed. And the WOMAC pain subscale score will also be summarized at each visit by treatment group on the FAS population. In addition,

change from baseline to week 16 in WOMAC pain subscale score, WOMAC physical function subscale score and PGA will be graphed by visit.

Weekly average and daily walking index joint pain using NRS

For the change from baseline in the weekly average and daily walking index joint pain using NRS, the same primary analysis method (MMRM) described in Section 8.2.1 will be analyzed. In addition, change from baseline to week 16 in weekly average walking index joint pain using NRS will be graphed by visit.

SF-36 / EQ-5D-5L

For the changes from baseline at each visit in SF-36 eight subscale summary scores and three component summary scores / EQ-5D-5L visual analogue scale(VAS) and utility index scores, the same primary analysis method (MMRM) described in Section 8.2.1 will be analyzed.

Proportions of subjects with improvement of 30%, 50%, 70% and 90% at each visit compared to baseline in WOMAC pain subscale score, WOMAC physical function subscale score and PGA

A generalized linear mixed-effects model (GLMM) by logit type for response variable will be used to evaluate these binary response variables. The denominator degrees of freedom for the test statistics of estimated parameters will be approximated using the Kenward-Roger method. The estimated response rate for each treatment group and placebo group, P value, and 95% confidence interval of the odds ratio of each of the MT-5547 1 mg q4w and MT-5547 1 mg q8w groups compared to the placebo group in each binary response variables will be calculated at each visit using this GLMM approach.

- The covariates: baseline and the interaction of baseline and measurement time point.
- The fixed factors: Treatment group, measurement time point, the interaction of treatment group and measurement time point, K-L grade (2-3 or 4), and evaluated joint location (knee or hip)
- Random factors: Intercept for subject

The SAS code planned for the analysis is outlined below.

[REDACTED]

[REDACTED]

[REDACTED]

[REDACTED]

[REDACTED]

[REDACTED]

Response rate based on the OMERACT-OARSI criteria at Week 16 compared to baseline

Responder analyses for OMERACT-OARSI will be summarized at each visit using the same GLMM approach in previous model.

Proportion subjects who used rescue medication

The proportion of subjects taking rescue medication in baseline and up to week 16 will be summarized by treatment group. Number of days on rescue medication during treatment period (Day 1 to Day 28, Day 29 to Day 56, Day 57 to Day 84, Day 85 to Day 112) will be summarized by treatment group. Number of weekly average usage of rescue medication will be summarized at each week by treatment group.

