The same method as that described in (a) Primary Analysis will be used to analyze the changes from baseline at each assessment time point in the WOMAC pain score, the WOMAC physical function score, the WOMAC stiffness score, the WOMAC total score, PGA, the NRS score for the average pain on walking in the evaluated joint over the past 24 hours, the SF-36, and the EQ-5D-5L.

A generalized linear mixed-effects model by logit type for response variable with baseline as a covariate and treatment group, K-L grade (2-3 or 4), and evaluated joint location (knee or hip) as factors will be used to evaluate the proportions of subjects achieving 30% and 50% improvements in their WOMAC pain scores at Weeks 16 and 24 compared to baseline as well as the OMERACT-OARSI response rate. A detailed description of this model is presented in the SAP.

The analysis methods used for the other secondary endpoints will be described in the SAP.

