2.2. Study Endpoint(s)

2.2.1. Efficacy Endpoint(s)

- (1) Primary efficacy endpoint
WOMAC pain subscale score (change from baseline at Week 16)
- (2) Key secondary efficacy endpoint
WOMAC physical function subscale score (change from baseline at Week 16)
- (3) Secondary efficacy endpoints
 - 1) Patient global assessment (PGA) (change from baseline at each assessment time point)
 - 2) WOMAC pain subscale score (change from baseline at each assessment time point)
 - 3) WOMAC physical function subscale score (change from baseline at each assessment time point)
 - 4) WOMAC stiffness subscale score (change from baseline at each assessment time point)
 - 5) WOMAC total score (change from baseline at each assessment time point)
 - 6) Proportions of subjects with 30%, 50%, 70% and 90% improvements in their WOMAC pain subscale scores compared to baseline (Weeks 16)
 - 7) Proportions of subjects with 30%, 50%, 70% and 90% improvements in their WOMAC physical function subscale scores compared to baseline (Weeks 16)

- 8) Numerical Rating Scale (NRS) score for the mean pain on walking in the evaluated joint (change from baseline at each assessment time point)
- 9) SF-36 (change from baseline at each assessment time point)
- 10) EQ-5D-5L (change from baseline at each assessment time point)
- 11) Improvement rate based on the Outcome Measures in Rheumatology Arthritis Clinical Trials-Osteoarthritis Research Society International (OMERACT-OARSI) criteria (at Weeks 16)
- 12) Amount of rescue medication used (number of days on which rescue medication was used, and amount [number of tablets] used)

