6. STATISTICAL CONSIDERATIONS

6.1. Descriptive Statistics

(1) Non-PK related

Continuous data will be summarized descriptively using the number in the analysis set (N), the number of observations (n), mean, standard deviation (SD), median, minimum and maximum. Categorical data will be summarized using frequency counts and percentages. The denominator for the percentages will be the total number of subjects in the treatment group and analysis population being presented, unless otherwise specified.

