A generalized linear mixed-effects model (GLMM) by logit type for response variable will be used to evaluate these binary response variables. The denominator degrees of freedom for the test statistics of estimated parameters will be approximated using the Kenward-Roger method. The estimated response rate for each treatment group and placebo group and 95% confidence interval of the odds ratio of each of the MT-5547 1 mg q4w and MT-5547 1 mg q8w groups compared to the placebo group in each binary response variables will be calculated using this GLMM approach.

- The covariates: baseline and the interaction of baseline and measurement time point.
- The fixed factors: Treatment group, measurement time point, the interaction of treatment group and measurement time point, K-L grade (2-3 or 4), and evaluated joint location (knee or hip)
- Random factors: Measurement time point for subject specific with covariance structure of unstructured

The sample SAS code planned for the analysis is outlined below.

[REDACTED]

Response rate based on the OMERACT-OARSI criteria at each assessment time point compared to baseline

Responder analyses for OMERACT-OARSI will be summarized at each assessment time point using the same GLMM approach in previous model.

Proportion subjects who used rescue medication

The proportion of subjects taking rescue medication in baseline and up to week 48 will be summarized by treatment group. The proportion of days on rescue medication use during treatment period will be summarized at each week by treatment group. Number of average usage of rescue medication will be summarized at each week by treatment group.

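### Responder endpoints are proportions of subjects, but the Week 16 SAP estimates subject-specific odds ratios from a random-intercept logit model, and the Week 68 SAP gives a different random structure for the same endpoints

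*SAP*

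**What the plan says.** Both SAPs list among the secondary endpoints (section 2.2.1) "Proportions of subjects with 30%, 50%, 70% and 90% improvements in their WOMAC pain subscale scores". The Week 16 SAP lists them for Week 16, and the Week 68 SAP for every assessment time point. Physical function has matching endpoints.

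Protocol 13.3.2 chooses the type of model, "A generalized linear mixed-effects model by logit type for response variable with baseline as a covariate", with treatment group, K-L grade and joint as factors. It names no random structure and leaves the detail to the SAP.

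The two SAPs use the same fixed effects and covariates but differ in the random part:

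- Week 16 SAP, 8.2.3: "Random factors: Intercept for subject". Reported: "The estimated response rate for each treatment group and placebo group, P value, and 95% confidence interval of the odds ratio", at each visit.
- Week 68 SAP, 8.2.1: "Random factors: Measurement time point for subject specific with covariance structure of unstructured". Reported: "The estimated response rate for each treatment group and placebo group and 95% confidence interval of the odds ratio".

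In each SAP the OMERACT-OARSI response uses the same model as the improvement thresholds. Neither SAP says whether its rates and odds ratios are subject-specific or population-averaged, and neither explains the change of random structure. The Week 16 SAP announces its code ("The SAS code planned for the analysis is outlined below"), but the code is redacted.

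**The concern.** A proportion of subjects is a population quantity. In a logit model with a subject random intercept, the treatment coefficient compares odds at the same value of the random effect. Because the logit link is not linear, that odds ratio differs from the odds ratio of the two population proportions. A rate read off at a random effect of zero is likewise not the proportion who respond.

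At stake is how the reported figures are read. A reader who sees a responder endpoint with an odds ratio beside it will take the odds ratio as describing the proportions. A reader who compares the Week 16 and Week 68 reports could find two Week 16 odds ratios for the same endpoint, with nothing in either plan to explain the difference.

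**Working it through.** **No planned figure to reproduce.** The documents give no responder rate, odds ratio or random-intercept SD for this trial. The SD σ below is an assumption, shown over a range.

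**Formulas.** Let expit(x) = 1/(1 + e^−x) and let Z be standard normal.

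- The subject-level logit η that gives population rate p solves E[expit(η + σZ)] = p, by Gauss-Hermite quadrature.
- Subject-specific odds ratio = exp(η_active − η_placebo).
- Rate back-transformed at random effect zero = expit(η).

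**Simple case: 70% against 50%.** The population odds ratio is (0.70/0.30)/(0.50/0.50) = 2.33. For p = 0.50, η = 0 at any σ, so the subject-specific odds ratio equals the active arm's odds at random effect zero.

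| σ | Subject-specific OR | 70% becomes OR/(1 + OR) | 30% becomes (by symmetry) |
|---|---|---|---|
| 1 | 2.77 | 73.5% | 26.5% |
| 2 | 3.99 | 80.0% | 20.0% |
| 3 | 6.19 | 86.1% | 13.9% |

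**Illustration from Table 3.3-1 (overseas study R475-PN-1227).** The Week 16 pain change on placebo was −2.43 (SD 2.38) from a baseline of 6.43. On 1 mg it was −3.49 (SD 2.06) from 6.33. With a normal approximation at the mean baseline, the rate for threshold t is Φ((mean fall − t × baseline)/SD). For example, placebo at 30% is Φ((2.43 − 0.3 × 6.43)/2.38) = Φ(0.21) = 58.3%.

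σ comes from an assumed latent within-subject correlation ρ through σ = √[(ρ/(1 − ρ)) × π²/3]. Values of ρ of 0.3, 0.5, 0.7 and 0.8 give σ of 1.19, 1.81, 2.77 and 3.63. The table uses σ = 1.81, and its last column covers the full range. Arrows run from the population value to the value at random effect zero. Differences were taken before rounding.

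| Improvement | Placebo rate, % | 1 mg rate, % | Difference, points | OR | OR, σ 1.19 to 3.63 |
|---|---|---|---|---|---|
| 30% | 58.3 → 62.8 | 78.0 → 87.4 | 19.7 → 24.5 | 2.53 → 4.09 | 3.21 to 9.68 |
| 50% | 37.1 → 30.5 | 56.3 → 59.7 | 19.2 → 29.2 | 2.18 → 3.37 | 2.71 to 7.15 |
| 70% | 19.2 → 10.2 | 32.4 → 24.2 | 13.2 → 14.1 | 2.01 → 2.83 | 2.38 to 5.32 |
| 90% | 7.9 → 2.7 | 14.2 → 6.3 | 6.3 → 3.6 | 1.92 → 2.41 | 2.12 to 3.97 |

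The odds ratio moves away from 1 in every row. The rates move away from 50%: five of the eight population rates are below 50% and would be understated. The difference between arms widens at the 50% threshold and narrows at the 90% threshold.

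**Overlap of the two SAPs.** Section 9.3 of the Week 68 SAP lists Week 16 among the WOMAC and PGA visits. The Week 16 responder odds ratio is therefore estimated once with a random intercept and once with an unstructured by-visit effect.

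**The case against.** *The subject-specific odds ratio is legitimate, and the protocol chose a mixed model.* Both are true. The estimate is valid for its own target, and replacing the model outright would be a matter of preference. What remains is that neither SAP names the target, while the endpoint is a population proportion.

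*The rate problem rests on redacted code.* This stands. If the program averages over the random effect, the rate problem disappears. The redaction is not a fault in the plan. The odds-ratio point follows from the stated model and does not depend on the code.

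*Observed percentages will be shown anyway.* Section 6.1 of the Week 16 SAP says "Categorical data will be summarized using frequency counts and percentages", and Protocol 13.3 has a similar rule for all variables analysed. This partly mitigates the rate point, although the responder text does not mention it. It does not change the odds ratio or reconcile the SAPs.

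*The Week 16 analysis has precedence.* Section 4.2 of the Week 16 SAP makes it the final efficacy analysis, and the Week 68 SAP (6.2) plans no formal tests. So no confirmatory conclusion is in doubt. Moreover, the Week 68 model includes later visits and re-estimates the variance, so identical random terms would not guarantee identical Week 16 values. That is fair, but it does not justify an unexplained difference in what is being estimated.

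*A stronger reading.* A reader might infer that the model overstates both the odds ratios and the response rates. The calculation does not support this for the rates, since those below 50% would be understated.

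**Conclusion.** The point holds as a minor one, in three parts resting on different ground:

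1. **Odds ratio.** For any non-zero effect and any random-intercept variance above zero, the Week 16 odds ratio is further from 1 than the odds ratio of the proportions. The direction follows from the model. The size (2.33 becoming 2.8, 4.0 or 6.2) rests on an assumed SD of 1, 2 or 3.
2. **Rates.** They are displaced away from 50% only if they are back-transformed at random effect zero, which cannot be seen.
3. **Two structures.** The mismatch between the SAPs is in the text and needs no assumption. The Week 68 wording could mean subject-level random visit effects or a residual covariance. On the second reading, the two reports would give different kinds of odds ratio for one endpoint.

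A reader might also infer that the trial's confirmatory result is exposed. It is not: the multiplicity procedure covers only WOMAC pain and physical function change at Week 16, and the responder endpoints lie outside it.

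**What to change.** Keep the protocol's repeated-measures logit mixed model and its covariates, and make three changes:

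- State one random or covariance specification and use it in both SAPs, saying plainly whether it is a subject-level random effect or a residual covariance.
- Report population-averaged response rates and treatment contrasts, obtained by averaging the model predictions over the random-effect distribution and the observed covariates.
- Label any odds ratio taken directly from the mixed model as subject-specific.

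A Week 16-only logistic model is not a good substitute. It would drop the earlier-visit data of subjects missing at Week 16, whom the sample-size section puts at 15%. Its odds ratio would also still be conditional on baseline, K-L grade and joint.

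The cost is a small programming change. The population-averaged odds ratios will be closer to 1 than those from the current specification. The confirmatory tests are untouched.
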